#### 6.3. EARLY WITHDRAWAL FROM THERAPY OR ASSESSMENT

# 6.3.1. Primary Reason For Discontinuation From The Study

A premature discontinuation will occur when a patient who signed the ICF ceases participation in the study, regardless of circumstances, before the completion of the study protocol procedures. Patients can be prematurely discontinued from the study for one of the following reasons:

- Adverse event (AE): Any significant AE that, in the opinion of the Investigator or concerned patient, is not compatible with study continuation.
- ➤ **Disease progression or worsening,** that according to the opinion of the Investigator is not compatible with study continuation..
- > Death.
- ➤ Lost to follow-up (Every effort must be made to contact the patient; a registered letter must be sent).
- Non-compliance with study drug: an indication that a patient has not agreed with or followed the instructions related to the study medication.
- ➤ Physician decision: a position, opinion or judgment reached after consideration by a physician with reference to the patient.
- ➤ Severe Protocol violation: an event or decision that stands in contrast to the guidelines set out by the protocol.
- > Study terminated by the Sponsor: an indication that a clinical study was stopped by Sponsor.
- ➤ Withdrawal of consent: study discontinuation requested by a patient for whatever reason.
- **Other reasons**, such as administrative reasons or pregnancy.

Before removal, each case should first be discussed with Dompé farmaceutici s.p.a.

The reasons for premature discontinuation from the study will be reflected on the Study Termination Record of the eCRF. Unless the patient has withdrawn consent, the follow up visit assessments should be performed as detailed in § 6.

The investigator should advise patients that prematurely discontinue on any therapies or treatments for their condition and refer them for further treatment as appropriate

Version No. 2.0 – Final 08/AUG/2019

# **6.3.2.** Discontinuation procedures

For any patient discontinuing the study following randomization, the Investigator will:

- ➤ ask the patient to undergo, as far as possible, a final medical visit (ETV) to examine the patient's health conditions. This examination will verify that all values tested at screening have remained within a clinically acceptable range (i.e., not clinically significant changes compared to screening).
- rrange for alternative medical care of the withdrawn patient, if necessary.
- report in the eCRF date and time of the last dose administration, and date and primary reason of study discontinuation.
- > record in the eCRF any follow-up if the patient is withdrawn for an AE. AE's should be followed until resolution.

# 6.3.3. Replacement procedure

Patients in this study who prematurely discontinue treatment will not be replaced.

It will be documented whether or not each patient completed the clinical study. If, for a patient, study treatment or observations are discontinued, the primary reason for discontinuation will be recorded.

### 6.4. END OF STUDY

Patients completing the double-blind treatment (Visits 1 Baseline to Visit 6 Follow up) will be considered completers.

For the purpose of this trial, the End of Study is defined as the date of the last visit of the last patient or upon completion of any follow-up procedure described in the protocol. The Investigator and the Sponsor have the right to discontinue the study at any time for reasonable medical and/or administrative reasons. As far as possible, this should occur after mutual consultation. Reasons for discontinuation have to be documented appropriately. In this event, no further patients will receive doses of the study drugs, and patients already having received a dose of study drug will not receive any further doses of the study IMP but will undergo all safety assessments scheduled after the last dose of study drug, up to an including the end of study examination.

Version No. 2.0 – Final 08/AUG/2019

#### 7. ENDPOINTS

#### 7.1. STUDY ENDPOINTS

The study objective is to assess the efficacy and safety of rhNGF when administered as eye drops to patients with moderate to severe dry eye.

Evaluation of the clinical efficacy and safety during and at the end of treatment with rhNG, will be performed on the basis of the following assessments at each time point.

Evaluations will be performed on day -8 (screening), day 1+2 (visit baseline), day 14±2 (week 2), day 28±2 (week 4 End of treatment), day 56±4 (week 8 Visit 4 FU), day 84±4 (week 12 Visit 5 FU), day 112±7 (week 16 Visit 6 FU), according to the schedule of evaluation (§ 2)

#### 7.1.1. Primary endpoint

• Change from baseline in Schirmer test I (without anesthesia) Vs week 4.

### 7.1.2. Secondary endpoints

- Change from baseline in Symptoms questionnaire (SANDE) scores for severity and frequency assessed at 4 weeks of treatment;
- Change from baseline in Schirmer II test (with anesthesia) Vs week 4;
- Change from baseline in Corneal and conjunctiva vital staining with fluorescein (National Eye Institute [NEI] scales) Vs week 4;
- Change from baseline in Tear Film Break up time (TFBUT) Vs week 4;
- Number of patients who experienced a worsening in symptom scores (SANDE) and/or NEI score >= 50% assessed at week 4;
- Quality of life (Impact of Dry Eye on Everyday Life (IDEEL) questionnaire;
- Patient global Impression of change (PGIC);
- EQ-5D-3L.

### 7.1.3. Exploratory endpoint

- Correlation between sign and symptoms scores;
- Proportion and frequency of preservative free artificial tears use (n° drops/day) during the treatment period;
- Frequency of preservative free artificial tears use (n° drops/day) during the follow up period.
- Change from baseline in Schirmer test I (without anesthesia) Vs week 2;
- Change from baseline in Symptoms questionnaire (SANDE) scores for severity and frequency assessed at 2 weeks of treatment;

- Change from baseline in Corneal and conjunctiva vital staining with fluorescein (National Eye Institute [NEI] scales) Vs week 2;
- Change from baseline in Tear Film Break up time (TFBUT) Vs week 2;
- Number of patients who experienced a worsening in symptom scores (SANDE) and/or NEI score >= 50% assessed at week 2;
- Change from baseline in goblet cells density Vs week 4

# 7.1.4. Safety endpoint

• Incidence and frequency of Treatment-emergent adverse events (TEAEs), assessed throughout the study.

# 7.1.5. Stratification according to absence /presence of Primary Sjögren's Syndrome

• The primary, secondary, explorative and safety endpoints (see 7.1.1, .7.1.2 7.1.3 & 7.1.4) will be also evaluated within each stratification subgroup (absence/presence of Primary Sjögren's Syndrome)..

Version No. 2.0 – Final 08/AUG/2019

#### 8. EVALUATION OF ADVERSE EVENTS AND SAFETY INFORMATION

#### 8.1. **DEFINITIONS**

#### **Adverse Event**

An **Adverse Event** (**AE**) is defined as any untoward medical occurrence in a patient or clinical investigation subject administered a medicinal product and which does not necessarily have a causal relationship with this treatment. An AE can therefore be any unfavourable and unintended sign (including an abnormal laboratory finding), symptom, or disease temporally associated with the use of a medicinal product, whether or not related to the medicinal product.

### **Adverse Drug Reaction**

An **Adverse Drug Reaction (ADR)** is defined as any noxious and unintended response to a medicinal product related to any dose. Any responses to a medicinal product means that a causal relationship between a medicinal product and an adverse event is at least a reasonable possibility, i.e., the relationship cannot be ruled out.

The definition covers also medication errors and uses outside what is foreseen in the protocol, including misuse and abuse of the product. For the purposes of IND safety reporting, "reasonable possibility" means there are facts (evidence) or arguments to suggest a causal relationship between the drug and the adverse event.. Adverse events are to be considered unrelated if the relationship to the study drug, as described in the table in § 8.2.1, is none or unlikely; whereas any AE reported in the study having a possible, probable or highly probable relationship to study drug will be considered as an ADR. The determination of expectedness should be made by the Sponsor on the basis of the IB.

# **Serious Adverse Event**

A Serious Adverse Event (SAE) is defined in line with (CFR - Code of Federal Regulations Title 21 Sec. 312.32) as any adverse experience that, in the view of either the Investigator or sponsor, meets any of the following criteria::

- results in death,
- is life-threatening (i.e. the patient was at immediate risk of death at the time of the event. It does not refer to an event which hypothetically might have caused death if it were more severe),
- requires inpatient hospitalization or prolongation of existing hospitalization.

NOTE: In general, hospitalization means that the individual remained at the hospital or emergency ward for observation and/or treatment (usually involving an overnight stay) that would not have been appropriate in the physician's office or an outpatient setting. Complications that occur during hospitalization are AEs. If a complication prolongs hospitalization or fulfills any other serious criteria, the event is serious. When in doubt as to whether "hospitalization" occurred, the event should be considered serious.

Version No. 2.0 - Final 08/AUG/2019

• results in persistent or significant disability/incapacity.

NOTE: The term disability means a substantial disruption of a person's ability to conduct normal life functions. This definition is not intended to include experiences of relatively minor medical significance such as uncomplicated headache, nausea, vomiting, diarrhea, influenza, or accidental trauma (e.g., sprained ankle) which may interfere or prevent everyday life functions but do not constitute a substantial disruption

- is a congenital anomaly/birth defect,
- is an important medical event.

NOTE: An important medical event is an event that may not result in death, be life threatening, or require hospitalization but may be considered a SAE when, based upon appropriate medical judgment, it may jeopardize the patient's wellbeing and may require medical or surgical intervention to prevent one of the outcomes listed in the definitions for SAEs. Examples of such medical events include allergic bronchospasm requiring intensive treatment in an emergency room or at home, blood dyscrasias or convulsions that do not result in patient hospitalization or the development of drug dependency or drug abuse

Pre-planned hospitalization or hospitalization for routine treatment or monitoring of the studied indication, not associated with any deterioration in condition are not considered to be SAEs (see Par. 8.3.2).

These events must be recorded in the AE page of the eCRF where a variable will be ticked to indicate that they are not SAEs.

Death shall always be reported as SAE and cause of death shall always be specified when known.

## **Unexpected Adverse Event/Reaction**

An AE or ADR is considered unexpected if it is not listed in the Investigator Brochure or is not listed at the specificity or severity that has been observed and listed in the Investigator Brochure. Events that are mentioned in the Investigator Brochure (section Reference Safety Information) as occurring with a class of drugs or as anticipated from the pharmacological properties of the drug, but are not specifically mentioned as occurring with the particular drug under investigation are considered unexpected (21 CFR312.32(a)).

# Suspected serious unexpected adverse reaction

A suspected serious unexpected adverse reaction (SUSAR) is defined as an adverse reaction that is both unexpected (not consistent with the applicable product information) and also meets the definition of a Serious Adverse Reaction.

As mentioned, the determination of expectedness should be made on the basis of the IB (section Reference Safety Information) .

Version No. 2.0 – Final 08/AUG/2019

# Adverse Events (AEs) of special Interest (Sight-threatening Events)

The following adverse events are considered to be of special interest and by default shall be reported as SAEs (medically important criteria):

- ➤ AEs that caused a decrease in visual acuity of >30 ETDRS letters or > +0.6 LogMAR (compared with the last assessment of visual acuity at the last visit) lasting >1 hour
- ➤ AEs that caused a decrease in visual acuity to the level of Light Perception or worse lasting >1 hour
- AEs that required surgical intervention (e.g., conventional surgery, vitreous tap or biopsy with intravitreal injection of anti-infectives, or laser or retinal cryopexy with gas) to prevent permanent loss of sight
- ➤ AEs associated with severe intraocular inflammation (i.e., 4+ anterior chamber cell/flare or 4+ vitritis)
- > AEs that, in the opinion of the Investigator, may require medical intervention to prevent permanent loss of sight.

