# 8.2. ADVERSE EVENT (AE) MONITORING

At visit 3 (end of treatment), visit 4 (FU), vist 5 (FU) and visit 6 (FU), after the patient has had the opportunity to spontaneously mention any problems, the Investigator or appropriate designee should inquire about AEs by asking the standard questions:

- "Have you had any health problems since your last study visit?"
- "Have there been any changes in the medicines you take since your last study visit?"

AEs should be reported for any clinically relevant change in concomitant condition(s) that is the result of an untoward (unfavorable and unintended) change in patient's medical conditions. Changes in any protocol-specific ocular or systemic parameter evaluated during the study are to be reviewed by the Investigator. In addition, the patient's responses to any questionnaire utilized during the study are to be reviewed by the Investigator. Any untoward (unfavorable and unintended) change in a protocol-specific parameter or questionnaire response that is clinically relevant is to be reported as an AE. These clinically relevant changes will be reported regardless of causality.

All AEs should be followed-up to determine outcome of the reaction.

In order to collect as complete as possible information in the clinical study database, all ADRs and SAEs ongoing at the time the subject's study participation ends should be evaluated within 10 days after the final visit. After this period, all unresolved ADRs and SAEs will be reported as "ongoing" in the eCRF.

Version No. 2.0 – Final 08/AUG/2019

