3.7. Study Procedures and Flowchart

| Study procedures | Screening (Day-8) | Visit 1 Baseline Day 1* | Visit 2 Week 2 | Visit 3 End of treatment Week 4 ^a | Visit 4 follow- up Week 8 ^a | Visit 5 follow- up Week 12 ^b | Visit 6 follow- up Week 16 ^c |
|--|----------------------|-------------------------------|----------------------|---|--|---|---|
| Informed Consent | X | | | | | | |
| Inclusion/Exclusion Criteria | X | X | | | | | |
| Pregnancy Test | X | X | | | | | X |
| Randomization | | X | | | | | |
| Demographics | X | | | | | | |
| Ocular and Systemic Medical History | X | | | | | | |
| Previous Ocular And Systemic Medications | X | X | | | | | |
| SANDE | X | X | X | X | X | X | X |
| IDEEL | X | X | | X | X | X | X |
| EQ-5D-3L | X | X | | X | X | X | X |
| PGIC | | | | X | X | X | X |
| BCDVA | X | X | X | X | X | X | X |
| External Ocular Examination | X | X | X | X | X | X | X |
| Schirmer test I | X | X | X | X | X | X | X |
| Slit Lamp Examination | X | X | X | X | X | X | X |

This document is confidential.

| Study procedures | Screening (Day-8) | Visit 1 Baseline Day 1* | Visit 2 Week 2 | Visit 3 End of treatment Week 4 ^a | Visit 4 follow-up Week 8 ^a | Visit 5 follow-up Week 12 ^b | Visit 6 follow-up Week 16 ^c |
|---|----------------------|-------------------------------|-------------------|--|---|--|--|
| TFBUT | X | X | X | X | X | X | X |
| Fluorescein staining (NEI scale) | X | X | X | X | X | X | X |
| Schirmer test II | | X | | X | | | X |
| Confocal microscopy to assess goblet cells density ^d | | X | | X | | | X |
| Corneal endothelium and stroma evaluation as per confocal microscopy ^e | | X | | X | | | X |
| Study drug dispensation | | X ^f | | | | | |
| Verify patient study medication dosing compliance | | | | X | | | |
| Concomitant Ocular And Systemic Medications | | | X | X | X | X | X |
| Frequency of preservative-free artificial tears use (n° drops/day) | | | X ^g | X ^g | X ^h | X ^h | X ^h |
| Check and retrieval of patient's diary | | | X ⁱ | X | X | X | X |
| Record AEs | X | X | X | X | X | X | X |

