8.4. Post Hoc Endpoint

Some correlation between sign and symptom scores could be computed for exploratory purpose.

This document is confidential.

9. Safety

The population used for safety analyses will be the Safety Set (SS). Safety will be assessed on the basis of adverse events (AEs).

Safety tables are presented in tables 14.1.5.1 and 14.1.5.2 and 14.3.1.1 to 14.3.2.4 ((see section15)

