| 16.2.6.2.5.2 | Quality of Life Impact of Dry Eye on Everyday Life (IDEEL) Questionnaire – Feelings | Randomized Set |
| 16.2.6.2.5.3 | Quality of Life Impact of Dry Eye on Everyday Life (IDEEL) Questionnaire – Work | Randomized Set |
| 16.2.6.2.5.4 | Quality of Life Impact of Dry Eye on Everyday Life (IDEEL) Questionnaire – Dry eye treatment satisfaction | Randomized Set |
| 16.2.6.2.5.5 | Quality of Life Impact of Dry Eye on Everyday Life (IDEEL) Questionnaire – Dry eye symptom bothers | Randomized Set |
| 16.2.6.2.6 | Patient Global Impression of Change (PGIC) | Randomized Set |
| 16.2.6.2.7 | EQ-5D 3L | Randomized Set |
| 16.2.6.2.8 | Preservative-free artificial tears use | Randomized Set |
| 16.2.6.2.9 | Goblet Cells Density as per Laser Scanning Confocal Microscopy | Randomized Set |
| 16.2.6.2.10 | Best Corrected Distance Visual Acuity (BCVDA) Test | Randomized Set |
| 16.2.6.2.11 | Slit Lamp Biomicroscopy | Randomized Set |

This document is confidential.

| Listing Number | Name | Analysis Set |
|-----------------------|--|---------------------|
| 16.2.6.2.12 | Corneal Endothelium and Stroma Evaluation as per Confocal Microscopy | Randomized Set |
| 16.2.6.2.13 | External ocular examination | Randomized Set |
| 16.2.7.1 | Adverse Events (Part 1) | Randomized Set |
| 16.2.7.1 | Adverse Events (Part 2) | Randomized Set |
| 16.2.8.1 | Urine pregnancy test | Randomized Set |

This document is confidential.

18. Appendices

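### BCDVA and slit-lamp findings are measured at every visit but only listed, so acuity loss enters the by-arm safety tables only through an investigator-recorded AE

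*Protocol*

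**What the plan says.** - **Collection.** SAP 3.7, like Protocol 2, schedules acuity at screening, baseline and Weeks 2, 4, 8, 12 and 16: "BCDVA | X | X | X | X | X | X | X". Slit-lamp examination has the same seven marks. Protocol 6.1 and 6.2 place both under the examination of both eyes at baseline and afterwards.
- **Objective and endpoint.** Protocol 3.1 and SAP 3.1 name efficacy and safety. The only safety endpoint (Protocol 7.1.4, SAP 4.4) is treatment-emergent AEs.
- **Analysis.** SAP 9 states: "Safety will be assessed on the basis of adverse events (AEs". SAP 17 contains "Best Corrected Distance Visual Acuity (BCVDA) Test" as Listing 16.2.6.2.10, slit-lamp biomicroscopy as Listing 16.2.6.2.11 and external ocular examination as Listing 16.2.6.2.13.
- **Events of special interest.** Protocol 8.1 lists sight-threatening events that are reported by default as SAEs. The first is "AEs that caused a decrease in visual acuity of >30 ETDRS letters or > +0.6 LogMAR", with the comparator and duration given as "compared with the last assessment of visual acuity at the last visit) lasting >1 hour". The others are "AEs that caused a decrease in visual acuity to the level of Light Perception or worse lasting >1 hour", events needing surgery to save sight, severe intraocular inflammation, and "AEs that, in the opinion of the Investigator, may require medical intervention to prevent permanent loss of sight".
- **General AE rule.** Protocol 8.2: "Changes in any protocol-specific ocular or systemic parameter evaluated during the study are to be reviewed by the Investigator". Any clinically relevant untoward change must then be reported as an AE whatever its cause.

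**The concern.** Acuity is the most direct objective measure of harm to sight in this trial, and it is taken in both eyes at every scheduled visit. A reader of the study report would expect to see how acuity moved from baseline in each arm. Under the SAP that reader gets a listing by patient and must do the comparison by hand.

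The tables by arm hold acuity loss only after two steps of judgement: an investigator decides that the change is clinically relevant, and then records it as an AE. Protocol 8.2 fixes no size and no reference visit for that decision. The standard questions to the patient ask only about the time since the last visit. A check against screening values is written only for patients who discontinue (Protocol 6.3.2). The numeric criterion in Protocol 8.1 does not close the gap, because its comparator is the last visit.

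At stake is whether a modest shift in acuity, or a loss that builds up over several visits, would be seen as a difference between rhNGF and vehicle. Protocol 10.3 provides no data monitoring committee, so the final tables are the main place where such a difference would show.

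**Working it through.** The plan states no figure on this point, so there is none to reproduce. The check compares the planned outputs and then does arithmetic on the criterion.

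**1. What is collected against what is tabulated**

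| Assessment | Scheduled visits (SAP 3.7) | Tables (SAP 15) | Figures (SAP 16) | Listing (SAP 17) |
|---|---|---|---|---|
| BCDVA | 7 | none | none | 16.2.6.2.10 |
| Slit lamp | 7 | none | none | 16.2.6.2.11 |
| External ocular examination | 7 | none | none | 16.2.6.2.13 |

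SAP 9.4 to 9.7 mark laboratory tests, vital signs, ECG and physical examination as not applicable. No subsection deals with ocular safety examinations.

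**2. How an acuity loss can reach a table by arm**

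SAP 9.3 and 15 tabulate treatment-emergent AEs (14.3.1.2.1), ocular AEs (14.3.1.3.1), serious AEs (14.3.1.6.1) and events of special interest (14.3.1.8.1). Each starts from a recorded AE. The acuity criteria in Protocol 8.1 also classify an AE that caused a loss. They do not screen the acuity data. So no route into a table starts from the measured value alone.

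**3. The numeric criterion**

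Inputs from Protocol 8.1: more than 30 letters or more than 0.6 logMAR. The implied scale is 0.6 / 30 = 0.02 logMAR per letter, so the two limits agree. There are five post-baseline visits (Weeks 2, 4, 8, 12, 16). The equal losses per visit below are illustrative assumptions. Cumulative loss = loss per visit × number of visits.

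| Letters lost per visit | More than 30 against the last visit? | First post-baseline visit more than 30 below baseline | Cumulative loss there |
|---|---|---|---|
| 5 | no | never (25 letters, 0.5 logMAR, at the fifth) | – |
| 10 | no | fourth | 40 letters, 0.8 logMAR |
| 15 | no | third | 45 letters, 0.9 logMAR |
| 20 | no | second | 40 letters, 0.8 logMAR |
| 30 | no | second | 60 letters, 1.2 logMAR |

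For example, 20 letters by Week 2 and 20 more by Week 4 give 20 + 20 = 40 letters, or 40 × 0.02 = 0.8 logMAR. Neither step exceeds 30. The same 40 letters in one interval does.

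The first row shows that a baseline reference at the same threshold would still not pick up moderate loss. Only a summary of change from baseline would.

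**4. What a summary by arm could say**

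Assume equal arms of 261 / 3 = 87 patients, all dosed and measured. If no patient in an arm fell in a given category of loss, the one-sided 95% upper limit for the rate would be 1 − 0.05^(1/87) = 0.034, or 3.4%. A table would give a statement of this kind. A listing does not.

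**The case against.** The strongest reply is that the documents already catch vision loss that matters. Protocol 8.2 makes the investigator review every ocular parameter and report any clinically relevant worsening, with no size limit and no last-visit limit. The general SAE definition in Protocol 8.1 covers lasting disability and important medical events. It applies independently of the special-interest list, with the same 24-hour reporting (Protocol 8.3, 8.4.1). Such events then appear by arm. This stands, and it rules out several stronger readings that a reader might be tempted by.

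- *Gradual loss is neither flagged nor compared between arms.* Not supported: it can be an AE, a special-interest event by investigator opinion, or an SAE, and all of these are tabulated by arm.
- *Stepwise loss never meets the numeric criterion.* Not supported. One interval may exceed 30 letters. For a single ongoing AE, the last visit could also be read as the last one before that AE began, so that 20 + 20 letters would count as 40. The text leaves this open.
- *The data cannot show a difference between arms.* Not supported: they are collected and listed. Only a planned summary is missing.
- *The plan contradicts itself.* It does not. Treatment-emergent AEs are the sole safety endpoint in both documents, and SAP 9 follows that.

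It is also true that nothing in the documents suggests that large stepwise loss is expected. Protocol 2.2 describes ocular AEs in previous studies as generally transient and mostly mild or moderate. That bears on how likely the problem is. It does not argue against tabulating a measurement taken at seven visits.

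**Conclusion.** The point holds as a gap in the planned safety outputs. Objective acuity and slit-lamp data are collected at all seven visits but have no table and no figure. Their only path into a comparison by arm is an AE that an investigator chose to record. The numeric special-interest criterion does not fill the gap. Under the visit-by-visit reading, losses of up to 30 letters in an interval fall outside it, and 40 letters from baseline can accumulate over two visits.

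The size is a matter of coverage, not of bias in a stated result. The loss patterns are illustrations, since the documents give no expected rate of acuity loss. The 3.4% limit assumes 87 measured patients per arm. Actual numbers will be somewhat lower if acuity is missing, for instance at the telephone visits allowed in SAP 2.1, which cover questionnaires, diaries and safety only.

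The conclusion does not extend to the special-interest definition itself. Whether that criterion should also refer to baseline is a clinical safety rule for the sponsor's safety function, and no contradiction in the documents forces a change.

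**What to change.** In SAP 9 and 15, before unmasking, add the following on the Safety Set:

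1. A table by arm and visit of BCDVA and its change from baseline, for each eye, using the baseline definition in SAP 6.2.1. Include the worst post-baseline value and the number of patients with a measurement at each visit.
2. Counts by arm of patients in each category of loss from baseline, with cut-offs chosen by the sponsor before unmasking.
3. A shift table from baseline for slit-lamp findings.

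Name one acuity scale for these tables. Inclusion criterion 5 uses decimal units and Protocol 8.1 uses letters and logMAR. The tables would be descriptive, so no error rate is affected. SAP 11 should record the addition.

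The cost is a few more outputs to program and check. No new data, visits or protocol amendment are needed.
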